### 4. Inclusion and Exclusion Criteria

- 4.1. A study investigator will screen patients with facial hair on the day of surgery in the preoperative holding area. We will enroll patients on the day of surgery and have them sign an informed written consent to participate in the study.

#### 4.2. Inclusion criteria

- Adult patients with perioral facial hair greater than 5 mm in length, and undergoing elective non-cardiac surgery inclusive of BMV.

4.3. Exclusion criteria are listed below. The exclusion criterion relating to known Tegaderm allergy will be screened for during verbal communication between the patient/participant and his/her doctor (who is also an investigator). All other exclusion criteria draw on information that is part of the routine pre-anesthesia assessment conducted for patients having general anesthesia.

- known allergy to Tegaderm product and/or its adhesive
- emergency surgery
- active or unstable cardiac disease
- ASA physical status\*  $\geq 4$ . ASA 4 physical status is a patient with severe systemic illness that is a constant threat to life; higher numbers indicate more severe morbidity.

\*ASA or American Society of Anesthesiologists physical status is a subjective designation by anesthesiologists used to describe allotted anesthetic and surgical risk to a patient undergoing an anesthetic based on the patients predetermined risk factors, disease burden and acute or life threatening pathology)

- external or internal active airway obstruction from tumor, abscess, or laryngeal edema,
- organic or non-organic oropharyngeal anatomical defects including history of neck radiation
- moderate to severe acute and chronic restrictive or obstructive lung diseases (including chronic obstructive pulmonary disease and asthma)
- patients that require rapid sequence intubation or with aspiration risk
- cervical spine injury, previously documented difficult mask ventilation or intubation
- $BMI \geq 50$
- Vulnerable populations: Children, prisoners, pregnant patients, cognitively impaired adults

### 5. Number of Subjects

5.1. This is a single-site study.

5.2. The data that would be required for a formal sample-size calculation with a reliable power estimate are not available. For this reason, this study will use a 2-phase enrollment study plan with an initial 25-patient external pilot to inform the sample size calculation for the main phase. The investigators will submit a modification to HRRC with the planned sample size for the main phase upon completion of the

## Tegaderm™ Placement for Bag Mask Ventilation in the Bearded Patient

external pilot. However, the investigators may begin enrolling main-phase patients immediately upon completion of the external pilot in order to maintain study momentum. The investigators will not enroll more than 25 main-phase patients before receiving HRRC authorization for the modification with the updated sample size.

5.3. The investigators are therefore requesting initial authorization to enroll up to 50 patients, with the expectation that a modification will be submitted to finalize the sample size. These additional participants (i.e. participants 26-50) are intended to allow the investigators to transition from the external pilot to the main phase while the modification for the final sample size is under consideration by HRRC.

## 6. Study Timelines

6.1. Describe time expectations:

Individual patients' participation will last less than five minutes.

Investigators anticipate that 12 to 18 months will be sufficient to enroll the planned 2-phase sample size.

Study completion (analysis and preparation of manuscripts and other presentations) is expected to take approximately 12 months after enrollment is completed.

## 7. Study Endpoints

7.1. *Describe the primary and secondary study endpoints.*

Primary outcome: Mask leakage, defined as the difference between average inspired and expired tidal volumes, as a percentage of inspired volume. Patients will serve as their own controls; the comparison is of the difference in leakage in the Tegaderm™ versus baseline conditions.

Secondary outcomes: 1. Difference in airway resistance between Tegaderm™ and baseline conditions, 2. Difference in peak inspiratory pressure between Tegaderm™ and baseline conditions, 3. Extent to which mask leakage change with Tegaderm™ depends on beard length.

7.2. *Describe any primary or secondary safety endpoints.*

If bag/mask ventilation is difficult and a Tegaderm™ not already in place, one will be placed in an effort to provide a better seal for the mask. If ventilation continues to be difficult, an Attending Anesthesiologist would attempt bag mask ventilation, consider placing an oral airway, and follow the difficult airway algorithm (6) by using supraglottic airway as a rescue device if deemed necessary. This event will be considered data and included in analyses.

## 8. Research Setting

8.1. *Describe the sites or locations where your research team will conduct the research.*

The research will be conducted in the main surgical suites of UNM Hospital.

*8.2. Identify where your research team will identify and recruit potential subjects.*

Potential subjects will be identified and recruited from investigators' regular patients at the UNM surgical suites, in pre-operative holding areas.

*8.3. Identify where research procedures will be performed including any laboratory analytics*

All research will occur in the UNM surgical suites.

## **9. Resources Available**

*9.1. Investigator qualifications:*

PI [name] MD is a board-certified anesthesiologist, Division Chief of Cardiac Anesthesiology and Professor at UNM. Other investigators include experienced clinicians, a PhD research specialist, and medical residents; all investigators' research duties are well within their usual job duties. All research procedures will be performed by personnel who have appropriate training, experience, and authorization.

*9.2. Medical decision-makers:*

All clinical decisions will be made by appropriate providers who are duly authorized and credentialed to do so.

*9.3. Other resources:*

- UNM's operating rooms handle a high caseload, and the investigators anticipate little difficulty in recruiting 60 relevant patients from among them in one calendar year.
- Engagement in research activities is an expected part of all investigators' job duties, so conducting this study is not anticipated to conflict with their clinical, scientific, or administrative duties.
- The UNM surgical suites are equipped with the personnel, supplies, and equipment necessary to respond to any eventuality that may arise as a result of participation in this study.

## **10. Prior Approvals**

10.1. The completed Departmental Review Form is included with the initial application for review of this protocol

10.2. This study does not involve ionizing radiation, biological specimens, or specific medications.

## **11. Multi-Site Research**

11.1. This is not a multi-site study.

## **12. Study Procedures**

12.1. *Provide a thorough description of all study procedures, assessments and subject activities in a logical and sequential format.*

## Tegaderm™ Placement for Bag Mask Ventilation in the Bearded Patient

After obtaining informed written consent, patients will be pre-medicated with 1–2 mg of midazolam prior to entry into the operating room. Subjects will be transferred to the operating room table where they will lie in the supine position with the head and neck placed in the sniffing position. Mask ventilation operators will be confined to anesthesiology residents, Clinical anesthesiologist assistants (C-AA), and C-AA students all of whom are familiar with bag mask ventilation. Mask ventilation will occur using a two-handed Thenar-Eminence (TE) grip without the addition of an oropharyngeal airway. All operators will be instructed on how to perform this technique prior to patient enrollment. We will use Pressure Control ventilation mode on Anesthesia Ventilator machine (Dräger Perseus A500) set at 10 breathes per minute, I:E time of 1:2 and peak inspiratory pressure of 20 Cm H2O. An external pneumotachograph device and sensors (Phillips Respironics NM3™ respiratory profile monitor; Respironics CAPNOSTAT® Mainstream CO2 sensor) (figure1) will be used to measure ventilation parameters (Vtins; ml, VtExp; ml, PPins; cm H2O, Res; cm H2O/L/sec) with collected data electronically saved to a dedicated flash drive associated with the pneumotachograph.

Prior to induction airway operators (Clinical Anesthesiologist Assistants, Anesthesiology Residents or Anesthesiologist attendings) will be trained to create an opening in the Tegaderm™. The steps of Tegaderm™ modification are as follows: 1.) Tegaderm™ will be folded in half. 2.) Two 1" cuts will be made forming an Isosceles triangle. 3.) Tegaderm™ is opened up, placed on the patient with the adhesive side down. Once placed the covering's structural backing is removed so not to create any creases, leaving a diamond shaped mouth hole allowing face mask perimeter to make contact with Tegaderm™.

[figure not shown]

Figure 1: <https://www.zoll.com/medical-products/defibrillators/r-series/etco2/>

Once standard ASA monitors are applied, an adult-sized oxygen mask (Medline™ Anesthesia Mask) will be placed over patient's face for pre-oxygenation with 100% O2 at a rate of 10 liters/minute until measured expired oxygen  $\geq 80\%$ . Immediately prior to administration of induction medications we will open the randomization envelope denoting which technique we will apply first. General anesthesia will be induced with 1–3 mcg/kg bolus of fentanyl, 1.5 mg/kg of lidocaine, 2–3 mg/kg propofol and 0.6–1mg/kg Rocuronium for ideal mask ventilation conditions. The study interval will be specified as the period beginning with apnea, anesthesia induction with neuromuscular

## Tegaderm™ Placement for Bag Mask Ventilation in the Bearded Patient

blockade to completion of one minute of mask ventilation with and without Tegaderm™ use. Patients will act as their own controls. Anesthesia induction and apnea will be defined as no voluntary respiratory effort and the absence of the eyelid reflex. Complete Neuromuscular blockade will be defined as Train of Four Ratio of **0/4** with neuromuscular monitoring at the *Corrugator Supercilii* muscle.

Once subjects are apneic and induced, **3** mask ventilation breaths will be administered in order to ‘acclimate’ the user to the mask and insure a proper thenar-eminence (TE) grip is being used. The randomized crossover trial will be started once complete neuromuscular blockade is verified. Every consecutive trial will alternate between starting with Tegaderm™ use and no alteration with patients acting as their own controls. Both no alteration and Tegaderm™ portion of exam will use the Resironics NM3™ (Resironics Deutschland, Herrsching, Germany) and CAPNOSTAT® 5 (Phillips Healthcare corporation, Eindhoven, The Netherlands) sensors to measure primary outcomes: Inspired tidal volumes (  $V_{t_{ins}}$ ; ml ), expired Tidal Volumes of End Tidal CO2 (  $V_{t_{Exp}}$ ; ml ) which will be used to determine predefined adequate BMV (Inspired Tidal Volume- Expired Tidal Volume difference of <15% defined as adequate) and secondary outcomes: within-patient differences between Tegaderm™ and no-alteration conditions for peak inspiratory pressures (  $PP_{ins}$ ; cm H2O ) and airway resistance (  $Res$ ; cm H2O/l/sec ) for 60 seconds, and facial hair grouping comparisons. The anesthesia machine will be set to deliver standardized pressure-controlled ventilation using common parameters: peak inspiratory pressure of 20 cm H2O, 10 breaths per minute, and an inspiratory-expiratory ratio of 1:2. These values are within common ranges used in standard practice, but may be modified during surgery as determined to be clinically appropriate by the attending anesthesiologist. General anesthesia will be maintained with sevoflurane 4-6% with 100% O2 at a rate of 6 liters per minute. Once data is gathered for the first part of the trial (no alteration or Tegaderm™), we will change our technique and collect data for second 60 seconds component of the trial in similar fashion to initial data collection.

If during the “no alteration” portion of the study we fail to establish a seal after 3 attempts at ventilation, an Attending Anesthesiologist would assess the stability of the patient and, if needed, attempt bag mask ventilation, incorporate airway adjuncts, and follow the difficult airway algorithm. If the patient is deemed stable a Tegaderm™ will be immediately applied over the patient’s face with a hole over the mouth. The same operator will perform TE grip MV technique in order to establish a seal and to collect our data. If a subject could not be rescue ventilated after application of Tegaderm™ placement, an Attending Anesthesiologist would follow the same rescue techniques as described above. Once the mask ventilation trial is completed, subjects will be intubated and maintained under general anesthesia as usual for their anticipated surgery.

In a hemodynamically unstable event the protocol will be halted in order to address the medical needs of the patient, the Attending Anesthesiologist would treat the event accordingly with the appropriate pharmacologic interventions. Once the patient is deemed medically stable the Attending Anesthesiologist would make the decision to

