## 1. Objectives

- 1.1. This is a prospective randomized cross-over controlled trial intended to assess the efficacy of applying Tegaderm™ over bearded patients' circumoral area to improve bag mask ventilation after induction of general anesthesia. We will use Pneumotachography to measure our primary outcome: the amount of airway leak during mask ventilation (Tidal Volume Inspired mL –Tidal Volume Expired mL). Secondary measures include peak inspiratory pressures (PPins; cm H2O) and airway resistance (Res; cm H2O/l/sec).
- 1.2. Hypothesis: Application of Tegaderm™ over patient with circumoral facial hair will significantly improve bag mask ventilation via improvement of facemask seal.

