### 3. Study Design

- 3.1. Our study design is a randomized prospective crossover trial in adult patients (>18 years), with circumferential perioral facial hair longer than 5 mm who will undergo elective non-cardiac surgery in the main adult operating rooms of the University of New Mexico Hospital.
- 3.2. Allocation concealment: Providers and subjects will be blinded to which method they will start with (control versus intervention) via envelope method prior to induction of general anesthesia.
- 3.3. Subjects who are consented to participate in the study will have facial hair measured as a continuous variable length (mm).
- 3.4. Mask ventilation operators will be confined to anesthesiology residents, anesthesiologist assistants (AA), and AA students all of whom are familiar with bag mask ventilation. Mask ventilation will occur using a two-handed Thenar-Eminence (TE) grip without the addition of an oropharyngeal airway. All operators will be instructed on how to perform this technique prior to patient enrollment. We will use Pressure Control ventilation mode on Anesthesia Ventilator machine (Dräger Perseus A500) set at 10 breaths per minute, I:E time of 1:2 and peak inspiratory pressure of 20 cm H2O, all of which are routine in our practice and within typical ranges at the national level. These are specified only in order to reduce practice variation not related to the intervention itself. An external pneumotachograph device and sensors (Phillips Respironics NM3™ respiratory profile monitor; Respironics CAPNOSTAT® Mainstream CO2 sensor) will be used to measure ventilation parameters ( Vtins; mL, VtExp; mL, PPins; cm H2O, Res; cm H2O/L/sec) with collected data electronically saved to a dedicated flash drive associated with the pneumotachograph .

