12.2.2. Study information

- 12.2.2.1. Level of the provider
- 12.2.2.2. Paralytic
- 12.2.2.3. Beard length (perioral)
- 12.2.2.4. Randomization result
- 12.2.2.5. Respiratory parameters

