## 13. Data Analysis

13.1. *Describe the data analysis plan, including any statistical procedures.*

Paired data (within patient differences in leakage,  $PP_{ins}$ , and airway resistance) will be assessed with paired t-test or Wilcoxon rank-sum test, depending on distribution normality. Beard condition groups will be compared on the primary outcome (leakage difference  $> 15\%$  significant) with ANOVA or Kruskal-Wallis test, also depending on distribution normality. Sensitivity analysis will provide percentage of observed standard deviation for detection of leakage difference and a traditional power analysis to provide the sample size required to detect significant outcome with our intervention.

13.2. *Provide a power analysis, if applicable*

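### Section 12.1 sets each patient's starting condition by two incompatible rules: a randomisation envelope and alternation from one patient to the next

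*Combined protocol and SAP*

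**What the plan says.** Several places describe a randomised order.

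- Section 1.1: "This is a prospective randomized cross-over controlled trial intended to assess the efficacy". Section 3.1 also calls the design randomised.
- Section 3.2, on allocation concealment: "Providers and subjects will be blinded to which method they will start with (control versus intervention) via envelope method prior to induction".
- Section 12.1, at the point just before the induction drugs: "we will open the randomization envelope denoting which technique we will apply first".
- Section 12.2.2 lists "Randomization result" among the items recorded for each patient.

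These do not all say the same thing. Sections 1.1, 3.1 and 12.2.2 support only the word randomised. Concealment by envelope is in 3.2, and the randomisation envelope with its time of opening is in 12.1.

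A few lines later, section 12.1 gives another rule: "Every consecutive trial will alternate between starting with Tegaderm™ use and no alteration with patients acting as their own controls".

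The protocol does not say how the sequence in the envelopes is produced, who prepares it, or which rule takes precedence.

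**The concern.** Both statements answer the same question: which condition does this patient receive first? Under the envelope rule nobody should know until the envelope is opened. Under the alternation rule, anyone who knows what the last patient received first knows what the next will receive first, and for that person the envelope conceals nothing.

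Foreknowledge is realistic here. The study has one site, and a treating investigator screens, recruits and consents patients on the day of surgery (4.1, 20.1, 25.1). That person could know the coming order before deciding whom to approach.

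If the alternation sentence governs, the study is not the randomised, concealed trial that sections 1.1 and 3.2 describe and could not properly be reported as one. If the envelope governs, the alternation sentence is an error that staff could follow by mistake, and different operators might then work to different rules.

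**Working it through.** **Does the sentence set order between patients?** Section 12.1 uses the word *trial* for one patient's session. It says "Once data is gathered for the first part of the trial (no alteration or Tegaderm™), we will change our technique", so a trial has two parts, one per condition. It also says "Once the mask ventilation trial is completed, subjects will be intubated", so a trial ends before that patient's intubation. Consecutive trials are then consecutive patients, and what alternates is the starting condition. The switch within a patient is described separately, in the first of these two quotes. The natural reading is alternation between patients.

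**Could both rules hold together?** Only in two ways.

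- A random list happens to alternate. For a simple random list of 25 (the pilot size in 5.2) the chance is 2/2^25 = 6.0 × 10⁻⁸.
- The envelopes are filled in alternating order. The order is then deterministic after the first patient, so it is neither randomised nor concealed.

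**How predictable is the order?** The protocol gives no figure to reproduce. For 25 patients, take a guesser who knows all earlier orders.

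- Alternation: the first order is a coin toss and the other 24 are known. (0.5 + 24)/25 = 24.5/25 = 98%.
- Simple 1:1 randomisation: 12.5/25 = 50%.
- Permuted blocks of size b, always guessing the under-represented order: expected correct guesses per block = b/2 + (2^b/C(b, b/2) − 1)/2. For b = 4 this is 2 + (16/6 − 1)/2 = 2.83, or 71%. For b = 6 it is 3 + (64/20 − 1)/2 = 4.1, or 68%. With sizes 4 and 6 mixed at random and the list cut at 25, simulation gives about 17 of 25 (68%).

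The alternation figure is an upper bound, because it needs knowledge of the previous order.

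**How much bias could follow?** Section 13.1 says the within-patient differences "will be assessed with paired t-test or Wilcoxon rank-sum test, depending on distribution normality". No period or sequence term is planned, so protection against a period effect rests on how order is assigned. With n1 patients starting on one condition and n2 on the other, the unadjusted paired mean contains (n1 − n2)/n times the period difference.

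| Order rule, n = 25 | Share of period difference passed on |
|---|---|
| Alternation, 13/12 | 1/25 = 4% |
| Blocks of 4 and 6 | mean 4.2%; worst case 14/11, 3/25 = 12% |
| Simple randomisation | mean 16% |

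At 50 patients (the initial cap in 5.3), alternation splits 25/25 and passes on nothing.

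The protocol gives no period difference. Assuming 2 to 10 percentage points of leak, 4% is 0.04 × 2 = 0.08 to 0.04 × 10 = 0.4 points, and 12% is 0.24 to 1.2 points.

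**The case against.** The strongest reply is that this is loose drafting with little consequence. *Alternate* may mean only that the order varies by envelope. *Trial* is not used consistently either: elsewhere in the protocol it means the whole study, and the disputed sentence ends with patients serving as their own controls, which is within-patient language. Each patient receives both conditions, so knowing the order cannot steer different patients into different arms. The operator learns the order before induction under either rule and can see the dressing. Alternation also balances the two orders slightly better than random blocks do. The 98% measures guessability and is not an error in any result.

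Much of this stands. The effect on the estimate is small, and the loose-wording reading cannot be ruled out. It does not rescue the text, though. The reference to the starting condition across consecutive trials points to order between patients, and staff who follow the sentence literally will alternate. Even on the charitable reading the sentence has to be rewritten and the sequence generation stated. The balance argument is correct but minor: with blocks of 4 and 6 the split was 13/12 in about 98% of simulated lists and never worse than 14/11.

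**Conclusion.** The concern holds. Sections 3.2 and 12.1 assign order by a concealed randomisation envelope, one sentence in 12.1 assigns it by alternation, and nothing says which governs. It should be fixed.

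The harm is to the claim of randomisation and concealment, more than to the size of the estimate. Under alternation up to 24 of 25 pilot orders could be foreseen. The bias in the paired mean through period imbalance would be about 0.08 to 0.4 percentage points of leak, which rests on the assumed period difference of 2 to 10 points. The conclusion that the rules conflict rests on no assumption about numbers, only on reading the sentence as setting order between patients.

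**What to change.** Bring sections 3.2 and 12.1 to one rule.

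- Delete the alternation sentence.
- State that order comes from a computer-generated random list. Permuted blocks of randomly varying size, such as 4 and 6, are one way to keep near-balance.
- Have the list prepared by an existing team member who does not enrol patients, and place it in sequentially numbered, opaque, sealed envelopes opened at the point 12.1 already names.
- If alternation is in fact used, do not describe the trial as randomised with concealed allocation.

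The cost is protocol wording and one generated list. Envelopes are already planned, and no patients or staff are added. Compared with alternation, the worst split in 25 patients goes from 13/12 to 14/11, with 13/12 still usual.

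### The hypothesis is better ventilation, but the primary outcome and the adequacy rule measure only mask seal, and expired tidal volume is recorded without being compared

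*Combined protocol and SAP*

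**What the plan says.** Section 1.2 states the hypothesis: the dressing "will significantly improve bag mask ventilation via improvement of facemask seal". The primary outcome is given in two places. Section 7.1 has "Mask leakage, defined as the difference between average inspired and expired tidal volumes, as a percentage of inspired volume"; section 1.1 has the same difference in millilitres, "the amount of airway leak during mask ventilation (Tidal Volume Inspired mL –Tidal Volume Expired mL". Section 12.1 adds a threshold for adequate bag mask ventilation: "Inspired Tidal Volume- Expired Tidal Volume difference of <15% defined as adequate". Inspired and expired volumes are named there as primary measures, but the only use stated for them is this threshold. No section sets a minimum expired volume or minute volume.

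Section 13.1 lists the within-patient comparisons as leakage, peak inspiratory pressure and airway resistance. Expired tidal volume is not on the list. Resistance is a secondary outcome in section 7.1 ("Difference in airway resistance between Tegaderm™ and baseline conditions").

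Three features of section 12.1 bear on the point. Ventilation is pressure-controlled at 20 cm H2O, with "10 breaths per minute, and an inspiratory-expiratory ratio of 1:2". The dressing has one hand-cut opening ("leaving a diamond shaped mouth hole allowing face mask perimeter to make contact with Tegaderm™"). The mask is held "without the addition of an oropharyngeal airway".

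**The concern.** Leak measures how well the mask seals. It does not measure how much gas the patient receives. Under pressure control the delivered volume is not fixed: it depends on the resistance and compliance beyond the mask. A dressing that stops gas escaping at the mask edge may leave the patient's volume as it was. If it also narrows the path to the airway, it may lower that volume.

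In either case the planned primary comparison would show a benefit, and the stated hypothesis would invite the conclusion that ventilation improved. Section 2.3 hopes the result will inform guidelines, so the difference between a better seal and better ventilation matters to the reader. The trial records the variable that separates the two and does not plan to compare it.

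**Working it through.** The plan gives no volumes, effect size or standard deviation, so there is no figure of its own to reproduce. The check asks what leak can and cannot show under the protocol's ventilator settings.

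**Inputs from section 12.1.** Pressure P = 20 cm H2O. Ten breaths a minute gives a 6 s cycle; a 1:2 ratio gives Ti = 2 s and Te = 4 s.

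**Assumed inputs.** Compliance C = 30 or 50 mL/cm H2O; resistance R between mask and lung from 10 to 200 cm H2O/L/s; leak conductance g = 5 (poor seal) or 1 (good seal) mL/s/cm H2O. Mask pressure is held at 20 during inspiration, and leak occurs only then.

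**Formulas.**
- τ = R·C/1000; a = 1 − exp(−Ti/τ); b = exp(−Te/τ)
- End-inspiratory volume = C·P·a / (1 − b(1 − a)); expired volume V = that × (1 − b)
- Leak volume L = g·P·Ti; leak % = 100·L/(L + V)

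**One case in full** (C = 30, R = 100, g = 1). τ = 3 s, a = 0.487, b = 0.264. End-inspiratory volume = 600 × 0.487 / (1 − 0.264 × 0.513) = 338 mL. V = 338 × 0.736 = 249 mL. L = 1 × 20 × 2 = 40 mL. Leak = 40/(40 + 249) = 13.9% (unrounded V).

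| Window | R | g | L, mL | V, mL (C=30) | Leak (C=30) | V, mL (C=50) | Leak (C=50) |
|---|---|---|---|---|---|---|---|
| Poor seal | 10 | 5 | 200 | 599 | 25.0% | 981 | 16.9% |
| Good seal only | 10 | 1 | 40 | 599 | 6.3% | 981 | 3.9% |
| Good seal, R ×5 | 50 | 1 | 40 | 419 | 8.7% | 483 | 7.6% |
| Good seal, R ×10 | 100 | 1 | 40 | 249 | 13.9% | 260 | 13.3% |
| Good seal, R ×20 | 200 | 1 | 40 | 131 | 23.4% | 132 | 23.2% |
| Poor seal, R ×10 | 100 | 5 | 200 | 249 | 44.6% | 260 | 43.5% |
| Poor seal, R ×20 | 200 | 5 | 200 | 131 | 60.4% | 132 | 60.2% |

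**Reading the table (C = 30).**
1. Pure sealing cuts leak from 25.0% to 6.3% and leaves expired volume at 599 mL. Seal improves; ventilation, in this model, does not.
2. With a fivefold rise in resistance, leak still falls by 16.3 points (25.0 − 8.7), while expired volume falls by 180 mL, or 30% (180/599).
3. With a tenfold rise, leak falls by 11.1 points and the window counts as adequate, while expired volume falls by 350 mL, or 58% (350/599).
4. On the millilitre scale of section 1.1, every good-seal row shows the same benefit, 200 − 40 = 160 mL, whatever happens to expired volume.
5. At a given seal, restriction raises the leak percentage: 25.0% to 44.6% to 60.4% with a poor seal, 6.3% to 13.9% to 23.4% with a good one. A window passes the 15% rule only if L < (0.15/0.85)·V = 0.176·V. At V = 249 mL that means a leak below about 44 mL; at V = 131 mL, below about 23 mL.

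**The case against.** The strongest reply is that the percentage is not blind to restriction. With pressure fixed, leak volume depends on the seal, and anything that reduces the patient's volume pushes the percentage up. Masking needs a tight seal together with a large rise in resistance, and a paired comparison of resistance is already planned and would probably show it. Section 12.1 has operators trained to cut the opening and avoid creases. Sections 7.2 and 12.1 escalate failed ventilation, section 7.2 counts that event as data, and section 14.2 reviews ventilation parameters and desaturation. The hypothesis itself names seal as the route, so leak is a coherent primary measure. All of this stands, and leak can remain primary.

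A reader might go further and infer that a patient receiving almost no gas would routinely pass as adequate, that the dressing is known to obstruct flow, or that a safety signal would go unseen. The documents support none of these. Row 5 of the table fails the 15% rule. No section reports restriction. The resistance comparison and the rescue and safety provisions give other ways to detect it. Nor does the adequacy label decide the trial: section 13.1 plans no comparison of the proportion adequate, so any misreading enters through the paired leak comparison.

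The reply does not cover the first case. When the dressing only seals, leak falls, resistance is unchanged, and peak pressure is set by the ventilator. None of the three planned comparisons then says whether the patient received more gas. Only expired volume does.

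**Conclusion.** The gap is real and moderate in size. The plan's claim is about ventilation, its measures are about seal, and the variable that links them is collected but not compared. In the illustration, falls in leak of roughly 11 to 19 percentage points accompany an expired volume that is unchanged, down 30% or down 58%.

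These sizes rest on assumed compliance, resistance and leak conductance and on a one-compartment model with constant mask pressure; with C = 50 the pattern is the same but the baseline leak is smaller. If a poor seal prevents the machine from reaching its set pressure, sealing could raise expired volume. The direction cannot be settled from the documents, which is the reason to measure it. Restriction by the dressing is a possibility that the trial should be able to rule out, not a finding. The primary outcome need not change.

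**What to change.** - **Sections 7.1 and 13.1:** add the within-patient difference in mean expired tidal volume (mL, Tegaderm minus no alteration) as a key secondary outcome. Analyse it within patient like the other paired outcomes, give a confidence interval, and report it with leak and resistance.
- **Conclusions:** write *improved seal* when only leak falls. Write *improved ventilation* only when the expired-volume interval supports it, with any non-inferiority margin fixed by the investigators in advance. Do not simply require that the observed mean not fall: if the true change is zero, the sample mean falls in about half of trials by chance, so a genuine seal benefit would be turned down that often.
- **Section 12.1:** either rename the 15% label *adequate seal*, or add an expired-volume condition whose value the investigators set and justify in advance.

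The cost is one more paired analysis of data already recorded, and a narrower conclusion if only leak improves. A margin, if used, should also enter the sample-size calculation after the pilot. A volume condition scaled to predicted body weight would need sex added to the data form; height is already collected.
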